4.3. Specifications for summary tables

For **continuous variables**, summary statistics will generally consist of sample size (N), number of missing values, arithmetic mean, standard deviation (SD), median, lower (Q1) and upper (Q3) quantile, minimum, and maximum. Summaries of PK and PD variables will, in addition, contain the geometric mean and the coefficient of variation.

Binary/categorical variables will be summarized and displayed in frequency tables showing sample size, absolute and relative frequencies.

In general, data will be included in summary tables stratified by randomized treatment group.

4.4. Specifications for plots

Unless otherwise specified, plots for continuous variables will present mean and SD for each randomized treatment group. LS means calculated from MMRM models will be presented as bars with whiskers representing 95% confidence intervals (CI). Binary endpoints will be presented as forest plots – with a point representing proportion of subjects meeting the endpoint and whiskers representing a 95% CI. Results from logistic regression will also take form of a forest plot – point with whiskers, where point represents odds ratio and whiskers confidence interval.

Time to remission will be presented graphically using Kaplan-Meier curve – a series of declining horizontal steps.

For safety analysis distribution of data will be presented as line and point and whisker plots (presenting mean and standard deviations) or boxplots (for variables with highly skewed distributions – such as CRP). For boxplot top and bottom of the box will represent lower and upper quartile respectively. Thick line in the middle of the box will be median. Whiskers will represent the lowest value at most $Q1+1,5*IQR$ (inter quantile range) and the largest value no further than $Q3+1,5*IQR$. Points will represent potential outliers. Treatment groups will be presented as separate panels within a figure.

Data will be shown for each randomized treatment group. Data collected during unscheduled visit will not be shown on plots unless otherwise specified.

4.5. Data listings

Data on listings will be listed as documented. Relevant generated and transformed variables will be listed next to the original data items. Any imputed value will be flagged.

In all listings the patient identifier and the randomized treatment group will be included. The patient identifier consists of the center and the patient number, additionally a flag specifying analysis set will be provided. In general, patient listings will be sorted by patient identifier and visit (if applicable), unless otherwise stated.

Patient listings of data that is collected independently from visits (e.g. adverse events, medical histories or medication) will be sorted by patient identifier, day of onset or start day of administration, duration and MedDRA preferred term or base substance name, respectively.

Missing values in the listings will be represented as NA (not available) for both text and numerical data. In case of partially missing dates (when day or day and month is unknown) missing data will be represented as series of 9s – for example 2022-03 will be presented as 2022-03-99. Any imputed data will be presented separately from raw data or flagged accordingly in order to be able to review all data as collected.

4.6. Handling of withdrawals, missing values and outliers

For the main analyses performed using the ITT and PP populations, data will be analyzed as observed during the study, no imputation rule will be applied.

A sensitivity analysis will be conducted for primary and secondary efficacy endpoints, whereby missing data are imputed using last observation carried forward method (LOCF) for continuous endpoints and non-responder imputation (NRI) method for binary endpoints.

In pharmacokinetic analyses, missing drug concentration data (no value, not available, NA) will be omitted from PK calculations. Drug concentration data below LLOQ will be treated in pharmacokinetic analysis as follows:

- If the concentration below LLOQ is recorded after the last measurable concentration in the dosing interval, then it is omitted from area calculations and elimination phase analysis.
- In other cases the concentration below LLOQ concentration value is set to zero.
- If an entire concentration-time profile below LLOQ, the profile will be excluded from the PK analysis.

For descriptive statistics of drug concentrations and calculation of PK parameters obtained directly from the observed concentrations (including C_{max} , $C_{min,ss}$, $C_{max,ss}$, C_{trough}) values below LLOQ will be set to zero.

A worst-case scenario will be used in the estimation of partial dates such as adverse events, medical history, rheumatoid arthritis history, smoking history or concomitant medications. That is, for an incomplete start date the first day of the month or the first month of the year will be used. For an incomplete stop date the last day of the month or the last month of the year will be used. If an estimated start date of event is earlier than the date of day 1 or the start date is completely missing, day 1 will be used, unless documented data does not allow for this interpretation.

If start date of smoking is completely missing, it will be replaced with the date of 18th birthday. For completely missing stop date of smoking, date when informed consent was signed will be used.

Whenever estimated dates will be calculated, the incomplete date will be listed and the study day will be calculated using the estimated date. These study days will be flagged as estimated in listings with a star (*) symbol.

For other situations regarding missing data not mentioned in this document, missing data will generally not be replaced or imputed.

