## 7.2. Safety Criteria

After the first dose of IMP, a subject may discontinue from the study for a variety of reasons. Treatment discontinuations may be initiated by a subject or may become medically necessary due to AEs, required treatment with a disallowed medication or therapy, or other reasons, as determined by the Investigator. If a subject discontinues treatment, their participation in the trial will be discontinued. Discontinued subjects should be encouraged to complete all early termination and Follow-up assessments with early termination assessments conducted as soon as possible after the subject is withdrawn.

An individual subject will be withdrawn from the study if:

- the subject withdraws his/her consent, which he is allowed to do at any time and without the need to justify his/her decision;
- the subject requires treatment with any medication known or suspected to interfere with the study medication;
- the subject is no longer able to participate for other medical reasons (e.g. surgery, adverse event);
- the subject – in spite of the earlier evaluation upon recruitment – is suspected or found not to comply with eligibility criteria;
- there is evidence or sound suspicion that the subject fails to comply with the protocol directives (compliance with the treatment schedule, non-adherence to dietary rules or other study restrictions that may have an influence on study results, non-attendance at study assessments);
- any other condition occurs which in the opinion of the Investigator no longer justifies or permits a safe participation of the subject.

Each patient has the right to withdraw from the study at any time without prejudice. The Investigator may discontinue any patient's participation when he/she feels it is necessary, for any reason including adverse events or Clinical Study Protocol violation. The patient should always be informed about the reason for his discontinuation. Reasons for the withdrawal of an individual patient from the study will be recorded by the Investigator in the Case Report Form and in the Clinical Study Report. In the case of withdrawal caused by an adverse drug reaction, the patient will be under observation until symptoms of the reaction have subsided.

In the case of emesis, an individual patient is to be withdrawn from the study if:

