**The patient reported outcome assessments:**

- Patient's Assessment of Arthritis Pain;
- Patient's Global Assessment of Arthritis;
- Health Assessment Questionnaire - Disability Index (HAQ-DI);

- SF-36 RAND;
- FACIT-fatigue scale.

Procedures that will be performed in case of early withdrawal include:

- DAS28-CRP/ ACR Assessments: Tender/Painful Joint Counts (68), Swollen Joint Count (66), Patient's Assessment of Arthritis Pain, Patient's Global Assessment of Arthritis, Physician Global Assessment of Arthritis, Health Assessment Questionnaire –Disability Index (HAQ-DI); SF-36 RAND; FACIT-fatigue scale;
- Questionnaire regarding possible SARS-CoV-2 infection;
- Review concomitant Medication and Treatments (RA and non RA): Current and prior medications (noting exclusions and required DMARD restrictions) taken with reasons and should include dose/duration;
- Vital signs: sitting blood pressure, pulse, and temperature;
- Perform complete physical Examination;
- 12-lead electrocardiogram;
- Collect blood samples for chemistry , haematology and coagulology laboratory assessments;
- Collect blood sample for local ESR assessment;
- Collect blood samples for RF, ACPA, CRP;
- Collect blood samples for lipid profile assessment;
- Collect urine sample for laboratory urinalysis and urine microscopy;
- Collect urine for urine pregnancy testing (women of childbearing potential, only);
- Confirm proper contraception is being used;
- Collect urine sample for toxicology tests (presence of drugs in urine), alcohol breath test;
- Review of the diary for compliance with daily diary completion;
- Collect used blisters;
- Serious and non-serious adverse events monitoring.

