4.11. Efficacy analyses

Unless otherwise specified all efficacy analyses will be performed on ITT data with sensitivity analyses performed on PP population and ITT population with data imputed using methods described in section 4.6. In addition, efficacy analyses will be performed in subgroups defined in section 3.2.

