4.11.2. Secondary efficacy endpoints

No correction for multiple comparisons are planned for secondary endpoints.

Proportion of subjects with DAS28-CRP remission (score < 2.6) in each study arm will be presented at any time as well as at Day 29, Day 57, Day 85 and Day 113. Proportion of subjects will be presented together with confidence intervals, difference from placebo with confidence interval and p value for comparison vs. placebo calculated using proportion test. Logistic regression model will be prepared to explain achievement of response at any time with following factors: treatment (placebo will be the reference value), country (Ukraine will be the reference value) and baseline DAS28-CRP score. Moreover, descriptive statistics for time to remission will be presented along with median time to remission estimated using Kaplan-Meier method. Each treatment arm will be compared to placebo using log-rank test.

Change from baseline in the Tender/Painful and Swollen Joint Count as well as change from baseline in PhGA will be analyzed using MMRM and performed as described for primary endpoint.

All of patient reported outcomes - change from baseline in PAAP, PtGA, HAQ-DI, SF-36 and FACIT-F will be only presented descriptively for each timepoint.

American College Rheumatology (ACR)20, ACR50, ACR70 and ACR90 responder rates will be presented in form of percentage of subjects that meets the criteria for the endpoint alongside 95% confidence interval calculated using Wilsons' method. Difference between CPL409116 arms and placebo will be presented together with confidence interval and p value calculated using proportion test. Logistic regression model will be prepared similar to the previously described endpoint of DAS28-CRP remission.

Supportive analysis will be performed on PP population, as well as ITT with imputation based on last observation carried forward (LOCF) for continuous variables and NRI method for binary endpoints and performed as described for the ITT population.

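### The main by-visit remission and ACR response rates leave withdrawn patients out of the denominator, and non-responder imputation is only a sensitivity analysis

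*SAP*

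**What the plan says.** **Handling of missing data.** For the main ITT and PP analyses, SAP 4.6 states that "data will be analyzed as observed during the study, no imputation rule will be applied". The same section names the "non-responder imputation (NRI) method for binary endpoints" as part of a sensitivity analysis. SAP 4.11 repeats the order: "all efficacy analyses will be performed on ITT data with sensitivity analyses performed on PP population and ITT population with data imputed". SAP 4.11.2 lists ITT with "last observation carried forward (LOCF) for continuous variables and NRI method for binary endpoints" as supportive.

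**Endpoints.** SAP 4.11.2 presents "Proportion of subjects with DAS28-CRP remission (score < 2.6) in each study arm" at Days 29, 57, 85 and 113 and also at any time during the study. For ACR, "responder rates will be presented in form of percentage of subjects that meets the criteria for the endpoint"; SAP 2.1.2 gives Weeks 4, 8 and 12. Differences from placebo are tested with a proportion test. No denominator is stated.

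**Withdrawal.** Protocol 7.2 says: "If a subject discontinues treatment, their participation in the trial will be discontinued". It adds that such patients should be encouraged to complete the early-termination and follow-up assessments. Protocol 4.1 and 4.6 provide an early-termination visit and two safety follow-up visits. In Protocol 9.4, the list opening "Procedures that will be performed in case of early withdrawal include" starts with the DAS28-CRP and ACR components. The SAP contains no rule that assigns these data to Week 4, 8, 12 or 16.

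**The concern.** SAP 3.1 makes ITT the main efficacy population. An observed-case proportion at Week 12, however, describes only the ITT patients who still have a Week 12 assessment. Protocol 10.3 itself expects some drop-out for lack of efficacy or adverse events and gives it a separate rule for the DAS28-CRP score, so withdrawal linked to outcome is foreseen.

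The missing-at-random assumption in SAP 4.11.1 belongs to the MMRM, which uses a patient's earlier visits. A proportion test at a single visit uses none of that information, so the assumption does not protect it.

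At stake are the headline remission and ACR rates and their comparison with placebo. With about 21 evaluable patients per arm, a few withdrawals can decide how these look.

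**Working it through.** **Inputs from the documents.** 25 patients per arm; 21 per arm evaluable; 16% drop-out (SAP 2.3, Protocol 1.1 and 11.2). Neither document gives response rates or drop-out by arm. Those used below are assumptions.

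**The plan's own figure.** 84/(1 − 0.16) = 100 in total and 21/0.84 = 25 per arm. The figure reproduces. It implies 4 of 25 patients per arm missing at Week 12.

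**Denominator.** Keeping missing patients in the denominator as non-responders would be NRI. The SAP lists NRI as a separate analysis, so the main by-visit denominator must be the patients with data at that visit. This is an inference, because the SAP does not state it.

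**Level.** With x responders among n ITT patients and a fraction d missing, the NRI rate is x/n and the observed-case rate is x/[n(1 − d)]. Their ratio is 1/(1 − d).
- At d = 0.16: 1/0.84 = 1.19. An NRI rate of 30% appears as 0.30/0.84 = 35.7%.
- At earlier visits fewer patients are missing, so 1.19 is the upper end under the planned drop-out.

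**Arm difference, equal NRI rates, assumed drop-out 24% and 8%.**

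| NRI rate in both arms | Observed, 24% drop-out | Observed, 8% drop-out | Difference |
|---|---|---|---|
| 20% | 0.20/0.76 = 26.3% | 0.20/0.92 = 21.7% | 4.6 points |
| 30% | 0.30/0.76 = 39.5% | 0.30/0.92 = 32.6% | 6.9 points |
| 40% | 0.40/0.76 = 52.6% | 0.40/0.92 = 43.5% | 9.2 points |

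**Illustrative counts, 25 per arm (active against placebo).** P values are without continuity correction, with the corrected value in brackets; the SAP does not say which applies.
- Drop-out 6 and 2: observed 12/19 against 7/23, difference 32.7 points, p = 0.034 (0.070). NRI 12/25 against 7/25, difference 20 points, p = 0.145 (0.244).
- Drop-out 2 and 6: observed 14/23 against 6/19, difference 29.3 points, p = 0.059 (0.114). NRI 14/25 against 6/25, difference 32 points, p = 0.021 (0.043).

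The two analyses can disagree, and the direction depends on which arm loses more patients.

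**Against the true rate.** Let q be the unknown response rate among the missing patients. The true rate is (1 − d) × observed + d × q. The observed-case error is therefore d × (observed − q), and the NRI error is −d × q. With d = 0.16 and an observed rate of 35.7%:
- q = 0: observed-case is 0.16 × 35.7 = 5.7 points too high and NRI is exact.
- q = 35.7%: observed-case is exact and NRI is 5.7 points too low.

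**The case against.** Several points on the other side stand.

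- **Withdrawn patients are not lost to all assessment.** A reader might infer from Protocol 7.2 that they have no later data. The documents do not support that: the early-withdrawal visit collects the full DAS28/ACR set, follow-up visits are planned, and the Day 113 visit includes these assessments. What is missing is a rule for using the early-withdrawal data.
- **Not every binary analysis is affected alike.** A reader might extend the point to all of SAP 4.11.2. Remission at any time and its logistic model can keep a withdrawn patient with any post-baseline score, and Kaplan-Meier censors rather than drops. The ACR logistic model is described only as similar to the remission one.
- **NRI is not neutral.** Where withdrawal is unrelated to response, as may hold for the mandatory stop after a positive SARS-CoV-2 test, observed-case is unbiased and NRI is too low. The NRI difference also moves with drop-out. With assumed observed-case rates of 60% and 30%, it is 0.60 × 0.76 − 0.30 × 0.92 = 18.0 points at 24% active and 8% placebo drop-out, and 0.60 × 0.92 − 0.30 × 0.76 = 32.4 points with the split reversed, while the observed-case difference stays at 30.
- **The effect will be visible.** NRI is prespecified, and SAP 4.7 tabulates early terminations and their timing.
- **The shift is modest against the noise.** At 30% with 25 per arm, the standard error of a difference is √(2 × 0.3 × 0.7/25) = 13 points, so 7 points is about half of it.

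These points limit the scope and strength of the concern. They do not give a reason for the analysis that leaves out withdrawn patients to lead.

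**Conclusion.** The point holds for the by-visit remission and ACR proportions and their differences from placebo. Under the planned 16% drop-out, observed-case rates run up to 1.19 times the NRI rates. Outcome-related, unequal drop-out can shift the arm difference either way, by about 7 points in the assumed 24% and 8% example.

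It is tempting to call the observed-case rates inflated and the shift spurious. Against NRI the excess is arithmetic. Against the true rates it holds only if withdrawn patients respond less often than those who stay, which the documents cannot show. The case for NRI as the lead is that it keeps every ITT patient in the comparison and counts withdrawal as failure, an outcome that can be defined for all of them.

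These are secondary endpoints without multiplicity control, and the primary DAS28-CRP MMRM is untouched. The change is a worthwhile, inexpensive improvement, not a condition for the trial's validity.

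**What to change.** In SAP 4.6 and 4.11.2, before unblinding:
- Make NRI the main analysis for the by-visit remission and ACR20/50/70/90 proportions and differences, with all ITT patients in the arm as the stated denominator.
- Keep the observed-case analysis as the sensitivity analysis and state its denominator.
- State whether early-withdrawal assessments are assigned to a scheduled visit and, if so, to which one. NRI then applies to patients still without data at that visit.

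Both analyses are already planned, so the cost is SAP wording and the order of tables, with no new data or visits. The downside is lower reported response rates, and conservative ones where withdrawal has nothing to do with response.

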4.2.4. Duration of rheumatoid arthritis

Duration of rheumatoid arthritis will be calculated as:

Duration of rheumatoid arthritis = (date of signature of ICF – date of rheumatoid arthritis diagnosis)/365.25,

where ICF is Informed Consent Form.

For partial dates imputation described in section 4.6 will be used prior to duration calculation.

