4.18. Additional analyses

After conclusion of main analyses, additional statistical analysis will be performed. Details of these analyses are beyond the scope of this document but a broad scope is described below.

Primary and secondary endpoints will be analyzed for subgroups based on two additional age categories: 18-37 vs 38-56 years old.

As part of additional analysis several endpoints will be considered:

- Change from Baseline in Disease Activity Score DAS28-ESR at Week 12
- Proportion of subjects based on category of response in change of DAS28-CRP score on week 12 (see section 4.2.8)
- Relationship between DAS28-CRP remission and ACR criteria.

Primary and secondary endpoints will be also analyzed in context of RA duration (<5 years vs. \geq 5 years).

All additional analysis will be performed on ITT population without imputation. If results are scientifically encouraging, PP and ITT with imputations will be also used to generate analyses.

5. Software and statistical programming

R programming will be performed according to Biostat standards as defined in PS11/2018 SOP “Data analysis” and related work instructions. The statistical analysis will be performed using the R statistical software package (Version 4.0.3 or later). Calculation of pharmacokinetic parameters will be performed in Phoenix WinNonlin 8.4 or later, except C_{trough} , accumulation ratio for $AUC_{(0-6h)}$, and accumulation ratio for C_{max} . PK parameters C_{trough} , accumulation ratio for AUC_{tau} , and accumulation ratio for C_{max} calculations and all other than PK parameters calculation analyzes will be performed using R statistical software package (Version 4.1.3 or later), based on the results obtained from the PK parameters calculations performed using WinNonlin or raw data on analyte concentrations. Pharmacodynamic analyses will be performed in R statistical software package (Version 4.1.3 or later).

6. References

Chow, S.C. and Liu, J.P. 2000. Design and Analysis of Bioavailability and Bioequivalence Studies, Second Edition, Revised and Expanded. Marcel Dekker, New York.

ICH Topic E9: Statistical Principles for Clinical Trials, 5 February 1998, adopted by CPMP, March 1998, issued as CPMP/ICH/363/96

ICH Topic E10: Choice of Control Group and Related Issues in Clinical Trials, adopted by CPMP, 20 July 2000, issued as CPMP/ICH/364/96

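### SAP Table 3 understates cigarettes per year by 12%, and the earliest-start, latest-stop date rule in SAP 4.6 can only lengthen RA, methotrexate and smoking durations

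*SAP*

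**What the plan says.** SAP 4.6 sets one worst-case convention for "partial dates such as adverse events, medical history, rheumatoid arthritis history, smoking history or concomitant medications". Under it, "for an incomplete start date the first day of the month or the first month of the year will be used". At the other end, "For an incomplete stop date the last day of the month or the last month of the year will be used". A further sentence begins "If an estimated start date of event is earlier than the date of day 1 or the start date is completely missing"; in those cases Day 1 is used, "unless documented data does not allow for this interpretation". Smoking has its own rule only when a date is fully missing: "If start date of smoking is completely missing, it will be replaced with the date of 18th birthday", and a fully missing stop becomes the consent date.

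Three derivations rely on this section. SAP 4.2.4 (RA duration) says "For partial dates imputation described in section 4.6 will be used prior to duration calculation", and 4.2.5 says the same for methotrexate. SAP 4.2.3 refers missing or partial smoking dates there as well. RA and methotrexate durations run from the start date to consent. Smoking runs to the stop date for a former smoker and to the screening visit for a current one.

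The three results are baseline summaries in SAP 4.8. RA duration also appears in SAP 4.18: "Primary and secondary endpoints will be also analyzed in context of RA duration", with the cut at 5 years.

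Table 3 in SAP 4.2.3 converts smoking records to cigarettes per day. It assumes 20 cigarettes per pack, a 30.4375-day month and a 365.25-day year, and gives 0.0024 for cigarettes per year.

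**The concern.** Taking the earliest start and the latest stop is a cautious choice when the question is whether an event could overlap treatment. When the two dates are subtracted to give a duration, the same choice can only make the answer too long, and errors do not cancel across patients. A cut-point applied to such a duration then misplaces patients in one direction only.

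The Table 3 entry is a separate matter. It disagrees with the table's own note and with the packs-per-year entry, so a programmer who follows the SAP as written gets wrong pack-years for any patient recorded in that unit.

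At stake are the accuracy of three baseline summaries by arm and of the RA-duration split in SAP 4.18.

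**Working it through.** **Table 3.** Multiplier = (1 for cigarettes, 20 for packs) / length of the period in days, using the table's own lengths and a 7-day week.

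| Unit | Printed | Recomputed |
|---|---|---|
| Cigarettes, day | 1 | 1 |
| Cigarettes, week | 0.1429 | 1/7 = 0.1429 |
| Cigarettes, month | 0.0329 | 1/30.4375 = 0.0329 |
| Cigarettes, year | **0.0024** | **1/365.25 = 0.0027** |
| Packs, day | 20 | 20 |
| Packs, week | 2.8571 | 20/7 = 2.8571 |
| Packs, month | 0.6571 | 20/30.4375 = 0.6571 |
| Packs, year | 0.0548 | 20/365.25 = 0.0548 |

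Seven of the eight entries reproduce. The packs-per-year entry implies 0.0548/20 = 0.0027 for cigarettes. The printed 0.0024 would need a year of 1/0.0024 = 417 days. Relative error: 0.0024/0.002738 - 1 = -12.3%. Example: 100 cigarettes a year for 20 years gives 100 × 0.0024/20 × 20 = 0.24 pack-years as printed and 0.27 with 0.0027.

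**Length of durations.** Assume true dates are spread evenly over the unknown period.

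- Year-only start placed at the beginning of January: too early by 0.50 year on average, at most just under 1. This applies to RA, methotrexate and a current smoker's start.
- Only the day missing: too early by 0.04 year on average, at most 0.08.
- Former smoker, both dates year-only: 0.5 at the start plus 0.5 at the stop, so about 1 year on average and at most just under 2. At 20 cigarettes a day that is about 1 pack-year.

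**The 5-year split.** With a year-only diagnosis date, the added time is uniform on 0 to 1 year. A patient whose true duration t lies between 4 and 5 years crosses the cut with probability t - 4. Nobody crosses downward. The share crossing is the integral of f(t)(t - 4) from 4 to 5, close to 0.5 × f(4.667), where f is the density of RA duration. The documents do not give f, so several forms were assumed:

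- Uniform 0.5 to 15 years: 0.5 × 1/14.5 = 3.4%.
- 0.5 plus exponential, overall mean 8 years: 0.5 × exp(-4.167/7.5)/7.5 = 3.8%.
- 0.5 plus exponential, overall mean 4 years: 0.5 × exp(-4.167/3.5)/3.5 = 4.3%.
- Log-normal, medians 5, 7 and 9 years, log-SD 0.8-0.9 (simulation): 4.8%, 4.3% and 3.9%.

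Simulation of the first three gives the same values. If only the day is missing, the share is about 0.3%.

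These are shares of patients with a year-only date. The documents do not say how many there will be. For 100 patients, using 3.4-4.8%:

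| Year-only share (assumed) | Patients moved up | Rise in mean RA duration |
|---|---|---|
| 10% | 0.3-0.5 | 0.05 year |
| 30% | 1.0-1.4 | 0.15 year |
| 50% | 1.7-2.4 | 0.25 year |
| 100% | 3.4-4.8 | 0.50 year |

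Under the log-normal forms, mid-year imputation gives a mean error of 0.00 year and misplaces 2.2%, 2.1% and 1.9%, in both directions.

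**Day 1 sentence.** Inclusion criteria 2 and 6 require at least 6 months of RA at screening and at least 12 weeks of methotrexate before it, so every estimated RA or methotrexate start precedes Day 1. Moving it to Day 1 would give a duration of consent minus Day 1, from -28/365.25 = -0.08 year to about 0.

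**The case against.** The date rule is not an adverse-event rule that strayed. SAP 4.6 names RA history and smoking history itself, so this is a prespecified convention, and the longest plausible disease or smoking burden can be defended as a worst case. Imputed values are flagged in the listings. That stands as a reason not to call the rule an oversight. It does not make the resulting durations unbiased.

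Four stronger readings are tempting, and the documents do not support them.

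- **The wrong multiplier distorts RA duration or the 5-year split.** It cannot. Table 3 feeds pack-years only, and only for records in cigarettes per year. For those records it acts against the lengthening from the date rule.
- **The Day 1 sentence produces zero or negative durations.** The exception for contradicting documentation, together with the entry criteria, should normally prevent this. What remains is loose wording that leaves the decision to the programmer.
- **About 4-5% of the trial is misclassified.** That would require every diagnosis date to be year-only.
- **Treatment comparisons are biased.** The dates precede randomisation, the rule is the same in every arm, and RA duration is not in the primary model of SAP 4.11.1. It is not among the SAP 3.2 subgroups either; the split belongs to the additional analyses run after the main ones.

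Mid-period imputation also has a weakness. A diagnosis recorded as 2022 with consent in November 2022 would become 1 July, about 4 months before consent and below the 6-month criterion. The earliest-date rule cannot do that to an eligible patient. This objection stands, and the replacement rule needs a bound.

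**Conclusion.** Both parts hold, and both are minor.

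The Table 3 entry is wrong by the table's own figures. Pack-years for patients recorded in cigarettes per year are 12% too low, and nothing else is affected.

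The date rule lengthens durations in one direction: about 0.5 year for a year-only RA or methotrexate start or a current smoker's start, and about 1 year for a former smoker with both dates year-only. This assumes true dates fall evenly within the year. At the 5-year cut it moves about 3-5% of patients with year-only dates upward and none downward, under assumed distributions of RA duration. With an assumed 30% of dates year-only, that is roughly one patient in 100.

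The effect is confined to descriptive baseline variables and one additional subgroup.

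**What to change.** Before database lock:

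1. In SAP Table 3, change 0.0024 to 0.0027.
2. In SAP 4.6, keep the worst-case rule for adverse events, medical history and concomitant medication.
3. For RA diagnosis, methotrexate start, and smoking start and stop dates, impute the middle of the known period (15th of the month; 1 July of the year), never later than consent. For RA and methotrexate, also keep the date compatible with the entry minimums: at least 6 months of RA (counted from diagnosis, as in 4.2.4) and at least 12 weeks of methotrexate before Screening.
4. State that the Day 1 sentence does not apply to RA, methotrexate or smoking dates. Leave fully missing RA or methotrexate dates missing, and keep the existing rules for fully missing smoking dates.

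The cost is one number and a few sentences in the SAP, with matching changes to the derivation programs. No new data are needed.
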